### **3.2.3.2. Imputation of Incomplete Dates**

An incomplete date occurs when the exact date an event occurred or ended cannot be obtained from a participant. The database contains data fields for month, day, and year. A date is incomplete if at least one of these three fields is not known. For many of the planned analyses, a complete date is necessary to determine if the event should be included in the analysis (i.e., if the event is treatment-emergent) or to establish the duration of an event. In such cases, incomplete dates will be imputed.

For the purposes of handling partially reported start and stop dates for an event the following algorithm will be applied:

- 1) For onset date:
  - a) If only the day part of the onset date is missing and occurs in the same month and year as the date of dose of study drug, the date of dose of study drug will be used as the onset date. Otherwise, the first day of the month will be used to complete the onset date.
  - b) If the day and month parts of the onset date are missing and occur in the same year as the dose of study drug, the date of the dose of study drug will be used as the onset date. Otherwise, January 1st will be used to complete the onset date.
  - c) If the onset date is completely missing, the date of the dose of study drug will be used as the onset date.
- 2) For end date:
  - a) If only the day part of the end date is missing, the last day of the month will be used to complete the end date.
  - b) If the day and month parts of the end date are missing, December 31st will be used to complete the end date.
  - c) If the end date is completely missing, the maximum of the participant’s end of study date or date of last contact will be used as the end date.

If any imputed start date causes the start date to occur after the end date, the end date will be used for the imputation of the start date. If any imputed end date causes the end date to occur prior to the start date of the event, the start date of the event will be used for the imputation of the end date.

### **3.2.4. Presentations by Study Visit**

When data are collected serially over time, individual data presentations may include by-study visit displays. By-study visit displays will only be summarized up to Week 104. Visits will be presented according to the nominal visit as obtained from the eCRF. If multiple observations are collected at a scheduled visit, the closest observation to the target day will be chosen. If two observations have equal distance from the target day but one is earlier and the other is later than the target day, the earlier observation will be chosen. Unscheduled assessments will be included in the listings.

### **3.2.5. Presentations by Worst Case**

When data are collected serially over time, individual data presentations may include “worst case on study” displays. In those situations, both scheduled and unscheduled assessments up to 104 weeks will be included.

### **3.2.6. Definitions and Terminology**

#### Age

Age is age at informed consent and is as captured on the eCRF.

#### Baseline Value

For purposes of analysis, the baseline value is defined as the last non-missing value obtained prior to calendar day of lerapoltrev infusion.

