**Laboratory assessments:**

- CBC with differential (Platelet count should be confirmed prior to catheter placement as well as at time of catheter removal and should remain consistent with inclusion criteria 11. Should the platelet count be less than  $125 \times 10^9/L$  on the day of catheter removal, a platelet transfusion should be administered and platelet count confirmed to be greater than  $125 \times 10^9/L$  prior to catheter removal)
- Pregnancy test for individuals of childbearing potential prior to infusion if no results on file within 48 h of but before planned infusion

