## 5.2.2 PVSRIPO Infusion (Day 0 or Day 1 [Visit 4])

Note: At the time of PVSRIPO infusion, emergency drugs, including epinephrine and diphenhydramine will be available and the neurologic status, oxygen saturation, and cardiac rhythm of the patient will be monitored. Drug infusion will occur in the neuro-intensive care unit (ICU) or neuro step down unit so that all other emergency facilities will be available.

- CBC with differential (Platelet count should be confirmed prior to PVSRIPO infusion as well as at time of catheter removal and should remain consistent with inclusion criteria 11. Should the platelet count be less than  $125 \times 10^9/L$  on the day of catheter removal, a platelet transfusion should be administered and platelet count confirmed to be greater than  $125 \times 10^9/L$  prior to catheter removal)
- PVSRIPO infusion should occur on the same day (Day 0) or the day after catheter placement (Day 1) to allow flexibility due to the longer infusion (6.5 hr) and complexity of scheduling the necessary components for the infusion (eg, operating room time, surgeon, support team, pharmacy time, radiology appointments). However, under extenuating circumstances (eg, unavoidable scheduling issues, delayed diagnosis from biopsy, issues with investigational product or other critical supplies), so long as the patient remains in the neuro-ICU or neuro step-down unit, the time from catheter placement to PVSRIPO infusion may be extended up to 72 h post-placement with Sponsor approval. This timeframe is in keeping with other agents delivered safely via CED via similar procedures for even longer periods of time, which was not associated with increased risk of infection [23, 24]. If infusion is delayed, it will be recorded in the eCRF and patient's source documents along with the rationale and the Sponsor's approval.
  - See **Section 6.2.4** for additional details pertaining to infusion of PVSRIPO

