#### Day 1 (Baseline)

Day 1 is the earliest day that study drug is initiated. Note that this is a change from the protocol where the first day of study drug administration was designated as Day 0.

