#### Treatment-emergent Adverse Event (TEAE)

A TEAE will be an AE that occurred during the study on or after catheter placement. Additionally, it is assumed that an AE which was reported to have started on Day 1 without an associated onset time occurred on or after catheter placement.

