**Treatment Period**

Treatment period is defined as the period from catheter placement to Week 104.

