**4.2.        SAFETY ANALYSIS SET**

The SAF includes all enrolled participants who had an infusion catheter placed. This will be the primary population used for the safety analyses. Participants in the SAF set will be analyzed based on the treatment received.

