### 5.8.2. Clinical Laboratory Assessments

AEs for clinical labs will be characterized according to CTCAE version 5 (when possible) and shift in grade from baseline to the worst post-baseline value will be summarized. Both scheduled and unscheduled assessments will be used to identify the worst post-baseline values.

The following categories of abnormal hepatic laboratory values will be evaluated for any occurrence among all post baseline assessments.

- Alanine Aminotransferase (ALT) and/or Aspartate Aminotransferase (AST)  $> 3 \times$  upper limit normal (ULN), Alkaline Phosphatase (ALP)  $< 2 \times$  ULN, and Total Bilirubin  $\geq 2 \times$  ULN

- AST > 3, 5, 8, 10, and 20 x ULN, and 5 x ULN for more than 5 weeks
- ALT > 3, 5, 8, 10, and 20 x ULN, and 5 x ULN for more than 5 weeks
- Total Bilirubin > 1.5 or  $\geq 2$  x ULN

Listings of all laboratory data with normal reference ranges, and CTCAE grades (when possible) will be provided.

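### Baseline is tied to the day of infusion but the safety window opens at catheter placement, so some laboratory shifts can be measured from the wrong reference value

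*SAP*

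**What the plan says.** Two SAP definitions turn on infusion. Under Baseline Value (3.2.6), "the baseline value is defined as the last non-missing value obtained prior to calendar day of lerapoltrev infusion". Under Day 1 (Baseline), "Day 1 is the earliest day that study drug is initiated". The baseline rule works by calendar day, so every value on the infusion date is excluded whatever its clock time.

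The other safety definitions turn on catheter placement. For adverse events, "A TEAE will be an AE that occurred during the study on or after catheter placement". For the treatment period, "Treatment period is defined as the period from catheter placement to Week 104". Concomitant medication, in the same section, also starts at placement. For the population (4.2), "The SAF includes all enrolled participants who had an infusion catheter placed".

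For laboratory grades (SAP 5.8.2), "shift in grade from baseline to the worst post-baseline value will be summarized", using scheduled and unscheduled results. No section defines post-baseline.

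On timing, Protocol 5.2.2 plans infusion for the day of placement or the day after, and "the time from catheter placement to PVSRIPO infusion may be extended up to 72 h post-placement with Sponsor approval". Protocol 5.2.1 schedules a Day 0 blood count: "Platelet count should be confirmed prior to catheter placement as well as at time of catheter removal".

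The protocol (7.1.3 and 8.4.5) starts treatment-emergent events at infusion. SAP Section 6 lists the relabelling of Day 0 as Day 1. It does not list the move of the treatment-emergent start to placement.

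**The concern.** The two reference points can be up to three calendar days apart, with a biopsy and catheter insertion between them. Which blood count serves as baseline then depends on when the infusion could be scheduled. A fall caused by the procedure could be a treatment-emergent event in the adverse-event tables and yet show no shift in the hematology table. Conversely, a count taken before any study procedure could be read as a change after baseline.

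Safety is a primary objective. Platelets are of particular interest, because Protocol 6.2.2.1 reports intracranial hemorrhage at catheter removal and names the platelet requirement as its mitigation. In a study planned for about 30 participants that did not reach that number (SAP Section 6), one or two misplaced shifts would be visible.

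**Working it through.** The plan gives no figure to reproduce. The check applies the SAP rules to a set of draw times.

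Inputs:
- Placement at 10:00 on Day 0 (assumed).
- Infusion 4, 24, 48 or 72 h later, which spans what Protocol 5.2.2 allows.
- Draw times as shown in the table (assumed).

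Rules:
- Study Day = draw date minus infusion date, plus 1 if the result is not negative.
- Baseline-eligible if the draw date is before the infusion date.
- In the safety window if the draw time is at or after placement.

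| Infusion after placement | Draw | Study Day | Baseline-eligible | In safety window |
|---|---|---|---|---|
| 4 h | Day 0 07:00, before placement | 1 | no | no |
| 4 h | Day 0 12:00 | 1 | no | yes |
| 24 h | Day 0 07:00, before placement | -1 | yes | no |
| 24 h | Day 0 12:00 | -1 | yes | yes |
| 24 h | Day 1 06:00 | 1 | no | yes |
| 48 h | Day 0 07:00, before placement | -2 | yes | no |
| 48 h | Day 0 12:00 | -2 | yes | yes |
| 48 h | Day 1 06:00 | -1 | yes | yes |
| 48 h | Day 2 06:00 | 1 | no | yes |
| 72 h | Day 0 07:00, before placement | -3 | yes | no |
| 72 h | Day 0 12:00 | -3 | yes | yes |
| 72 h | Day 1 06:00 | -2 | yes | yes |
| 72 h | Day 2 06:00 | -1 | yes | yes |
| 72 h | Day 3 06:00 | 1 | no | yes |

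A coherent pair of rules would put each value in exactly one of the last two columns. Of the 14 rows, 7 do so. Six are in both (1 + 2 + 3 at 24, 48 and 72 h) and one is in neither (same-day, before placement). These counts reflect the chosen draw times and are not frequencies among patients.

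1. *Later-day infusion.* In the six double rows the value follows the procedure. Being later, it displaces the pre-placement count as baseline.
2. *Same-day infusion.* The pre-placement count is barred from baseline, which falls back to Screening Period 2 (Day -7 to -1). The count carries Study Day 1. Without a definition of post-baseline, nothing excludes it from the worst-value search.
3. *Untimed adverse events.* The SAP assumes that an event on Day 1 without an onset time followed placement. Day 1 is the infusion day, so the assumption does not address an untimed event on an earlier placement day.
4. *Catheter placed, never infused.* There is no infusion date, so the baseline rule has nothing to refer to.

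If baseline is instead any draw before placement, each 07:00 value is eligible and outside the window, and every other value is the reverse. No row is then in both columns or in neither.

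**The case against.** Much of the opposing case stands, and it limits the size of the problem.

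- *A reader might infer that every Safety Set participant with a Day 0 count is affected.* The documents do not support that. With a later-day infusion, the pre-placement count remains baseline unless another value is recorded before the infusion day. Few such values are scheduled, and Protocol 5.7.3 does not require standard-care tests to be reported unless linked to an adverse event. The count that Protocol 5.2.2 asks for before infusion is excluded by the calendar-day rule if drawn on the infusion day. However, results linked to adverse events must be recorded, so the values that do enter the gap may well be abnormal.
- *A reader might infer that the SAP classes the same-day pre-placement count as post-baseline.* It does not say so; the term is undefined. To alter the worst grade, that count would have to be graded worse than every later value to Week 104, and to appear as a worsening it would also have to be worse than baseline. The eligibility limits on platelets, hemoglobin and neutrophils make this uncommon.
- *A reader might infer that catheter-only participants are certainly in the Safety Set.* SAP 4.2 requires a catheter and not an infusion, but it also requires enrollment. SAP Table 1 (footnote 2) calls a patient who is not infused a screen failure, and SAP 4.3 gives a failed biopsy at placement as an example of one. Membership is ambiguous.
- *A reader might infer that an untimed event on an earlier placement day is not treatment-emergent.* Compared by date, the main rule can still include it. The defect is only that the stated assumption is keyed to another day.
- *A reader might expect laboratory and adverse-event tables to match.* They need not, since only clinically significant abnormalities are reported as adverse events (Protocol 7.1.1).

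There is also a case for the calendar-day rule. Platelets are checked before placement and again at catheter removal. If both draws fall on Day 0 without times, the rule excludes both, whereas a placement anchor cannot tell them apart. In addition, the placement count may be transfusion-supported (inclusion criterion 11). Both points bear on how the fix is worded; neither removes the mismatch.

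**Conclusion.** The concern holds in limited form. The SAP's own definitions use two anchors, and the permitted interval between them allows a post-procedure value to become baseline and bars a same-day pre-procedure count from being baseline. The first effect needs a later-day infusion and a recorded value in between. For the same-day count to enter the worst-value pool as well, the undefined term would have to be programmed that way. Both are possible rather than certain. The documents do not say how many infusions were delayed, how many in-between values exist, or how many participants had a catheter but no infusion.

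The impact is confined to descriptive safety summaries, mainly hematology shifts, because the blood count is the panel in the shift tables that is scheduled on Day 0. ORR and DOR are not affected, since the baseline MRI precedes placement (Protocol 5.7.2), and OS runs from infusion. The plan should be corrected, but this does not threaten the efficacy conclusions.

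**What to change.** In SAP 3.2.6, for Safety Set summaries, define baseline as the last non-missing value before catheter placement and post-baseline as any value after placement. Where the draw time is missing, accept a placement-day value as baseline only if its record is identified as pre-placement, and otherwise exclude it from baseline. Key the untimed adverse-event assumption to the day of placement. In SAP 4.2, state whether catheter-only participants belong to the Safety Set and, if so, apply the same baseline to them. In SAP Section 6, list the move of the treatment-emergent start from infusion to placement.

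The cost is a few sentences and a small programming change. Catheter placement already has a listing (16.2.5.1.1), but the documents do not show whether draw and placement times are captured, so the rule relies on recorded times or visit labels. A pre-placement platelet count may be transfusion-supported and should be flagged in the shift table.

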#### Day 1 (Baseline)

Day 1 is the earliest day that study drug is initiated. Note that this is a change from the protocol where the first day of study drug administration was designated as Day 0.

#### Study Day

Study Day is defined relative to Baseline (Day 1). Thus, the study day of an event is calculated as:

$$\text{Study Day} = \text{event date} - \text{date of Day 1} (+ 1, \text{if event date} \geq \text{date of Day 1}).$$

#### Study Visit

Study Visit is the nominal visit as recorded on the eCRF.

#### Change from Baseline

Change from baseline for a given endpoint is defined as the Study Day X value minus the Baseline Value.

#### Days on Study

Days on study is the number of days from Day 1 to the date of study completion as recorded on the End of Study eCRF page.

#### Adverse Event

An AE is an untoward or medical occurrence associated with the use of study treatment (drug, biologic, or device) in clinical investigation participants, which does not necessarily have a causal relationship with the study treatment. An AE can therefore be any unfavorable and unintended symptom, sign, disease or condition, or test abnormality (although diagnosis should always be reported as the AE if known) regardless of the relationship to study treatment. AEs that do not meet the definition for a serious AE (SAE) are considered non-serious AEs.

#### Treatment-emergent Adverse Event (TEAE)

A TEAE will be an AE that occurred during the study on or after catheter placement. Additionally, it is assumed that an AE which was reported to have started on Day 1 without an associated onset time occurred on or after catheter placement.

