Determination of Sample Size	
Based on an interim summary of the Phase 1 study data of PVSRIPO in rGBM (Pro00031169), an ORR of 11.5% was demonstrated (7/61 patients). With 30 subjects treated in this study, there is >75% power to demonstrate a 20% or greater improvement in ORR with the addition of pembrolizumab (ORR > 31%, two-sided P<0.05).
 
The planned evaluable sample size of 30 patients will allow initial assessment of the anti-tumor response via the criteria noted in Table 3 and survival over time, to inform future study adaptations and/or the sample size and study design of new trials. The design will also allow for assessment of the efficacy, safety and tolerability of PVSRIPO plus pembrolizumab, relative to accumulated experience with PVSRIPO alone (eg, [5], data on file, Istari) and published or other data available with pembrolizumab alone in patients with rGBM (eg, [3]).

Study and Treatment Duration	
Maximum planned duration of follow-up: Up to 24 months (104 weeks). Participants achieving 24 months of follow-up may be offered participation in a roll-over protocol or other mechanism for longer-term follow-up.
 
Planned treatment duration:
 
 
Single PVSRIPO infusion at baseline (retreatment allowed for qualifying patients (ie, no ongoing AE <math>\geq</math> Grade 2 related to peritumoral edema, tolerated initial PVSRIPO infusion well) with enhancing disease <math>\geq</math> 6 months from initial PVSRIPO infusion (with or without post-infusion resection <math>\geq</math> 4 weeks after retreatment); see Section 3).
 
Pembrolizumab (200 mg IV infusion), q 3 weeks up to Week 104 (maximum of approximately 102 weeks of treatment), or until irAE meeting criteria for discontinuation or confirmed progression via criteria noted in Table 3).
 

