### **3.2      Delay in pembrolizumab administration for ongoing peritumoral or cerebral edema (or other TEAE/reasons)**

Peritumoral edema may be associated with PVSRIPO treatment and there is potential for the same after immune checkpoint inhibition. As such, the first planned dose of pembrolizumab (scheduled 2 weeks after PVSRIPO infusion) will be delayed by up to two additional weeks in participants with any ongoing  $\geq$  Grade 3 PTE or CE or  $\geq$  Grade 2 AEs related to PTE or CE following PVSRIPO infusion requiring active treatment, such as new or worsening neurologic signs and symptoms (eg, hemiparesis requiring  $\leq 4$  mg/day dexamethasone or seizure requiring anti-epileptics), until such events resolve to  $\leq$  Grade 1.

If such events have not resolved to  $\leq$  Grade 1 by 4 weeks post-PVSRIPO infusion, or the patient has not received pembrolizumab for any reason by 4 weeks post-PVSRIPO infusion, the participant will not receive pembrolizumab under this trial and will be replaced. If a participant requires  $> 4$  mg/day of dexamethasone or equivalent prior to the first dose of pembrolizumab, the

participant will not receive pembrolizumab under this trial and will also be replaced. These replaced participants will not be considered in the initial DLT assessment of the treatment with PVSRIPO and pembrolizumab.

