#### **8.4.5 Safety Analysis**

The full safety analysis set will include all patients who were administered at least one dose of the PVSRIPO. The safety of study-required pre-infusion procedures including catheter placement, will also be summarized.

Separate summaries will be prepared for the primary safety analysis set, which is patients who received PVSRIPO and  $\geq 1$  dose of pembrolizumab. Patients who received PVSRIPO alone will be summarized separately (secondary safety analysis).

Summaries of TEAE will begin at the time of PVSRIPO infusion. Adverse events considered related to screening or other pre-infusion procedures that are not SOC (eg, PV booster, biopsy prior to infusion, catheter placement without PVSRIPO infusion) will be summarized separately (screening data set).

All safety endpoints for patients receiving PVSRIPO and  $\geq 1$  dose of pembrolizumab may be summarized overall and by the number of pembrolizumab treatments received while on study (eg, 1, 2 to 3, 4 to 6, etc.).

Adverse events will be summarized by highest grade per patient and by attribution according to CTCAE v5.0, using the latest version of MedDRA preferred term as event category and MedDRA primary system organ class body term as Body System category. Unless otherwise stated, adverse events will be displayed in terms of frequency tables by treatment group by decreasing frequency. Each patient will be counted only once within each preferred term or system organ class. If a patient experiences more than one AE (or laboratory value) within a preferred term or system organ class for the same recording period, only the AE with the strongest relationship or the worst severity, as appropriate, will be included in the summaries of relationship and severity.

Events meeting the criteria for a DLT or SAE, leading to discontinuation, resulting in death, etc., will be reported in additional summaries. Changes from baseline over time and abnormal laboratory values, vital signs and NANO and KPS will also be reported.

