### 1.1. **STUDY OVERVIEW**

This is an open-label, single-arm, non-randomized study characterizing the efficacy, safety, and tolerability of lerapolturev delivered via intratumoral infusion followed by pembrolizumab in patients with recurrent glioblastoma (rGBM). Approximately 30 eligible participants, 18 years of age or older, are planned to be enrolled and treated with lerapolturev and at least one dose of pembrolizumab in this study. The maximum planned duration of follow-up in this study is up to 24 months (104 weeks), and consists of the following treatments:

- Single lerapolturev infusion on Day 0
  - Note: retreatment with lerapolturev is allowed for qualifying participants who progress  $\geq$  6 months from initial lerapolturev infusion
- Pembrolizumab (200 mg intravenous (IV) infusion) initiated 14 days after lerapolturev infusion (up to 28 days, if necessary), given every 3 weeks, through Week 104 (23.5 months of treatment) or until immune-related AE (irAE) meeting criteria for dose interruption/discontinuation or confirmed progression (must consider clinical and radiographic assessments)

The study will occur in the following periods:

- Screening Period 1: Between 1 and 6 weeks prior to catheter placement
- Screening Period 2: Within 7 days prior to catheter placement
- Catheter Placement and Biopsy (if required) Period: Day 0
- Lerapolturev Infusion Period/Baseline: Single lerapolturev infusion on Day 0 or Day 1 (unless extension granted by Sponsor)
- Post-lerapolturev Infusion, Pembrolizumab Treatment and Follow-up Period: pembrolizumab starting at Week 2 (up to Week 4, max) and every 3 weeks thereafter, to a maximum of Week 104 (approximately 23.5 months maximum pembrolizumab treatment duration)

The study may be adapted or expanded in one or more larger cohorts of participants, in consultation with the Data and Safety Monitoring Board (DSMB), based on interim review and considering the totality of the study data.

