### 5.8.1. Adverse Events

AEs will be mapped to a Medical Dictionary for Regulatory Activities (MedDRA) version 23.1 by system organ class and PT. If a participant experiences multiple events that map to a single PT, the greatest severity and strongest assessment of relation to a study drug will be assigned to the PT for the appropriate summaries. AE severity will be assessed according to the CTCAE version 5. If CTCAE grading does not exist for an AE, the severity of the AE will be graded as mild (1), moderate (2), severe (3), life-threatening (4), or fatal (5).

The number of participants for the following groups will be summarized by overall:

- Any TEAE
- Any TEAE related to a study drug or catheter with sub bullets for TEAEs related to catheter placement, lerapolturev or pembrolizumab
- Any TESAE
- Any TESAE related to a study drug or catheter with sub bullets for TESAEs related to catheter placement, lerapolturev or pembrolizumab
- Any DLTs
- Any AESIs for lerapolturev
- Any irAEs for pembrolizumab
- Any TEAEs leading to discontinuation of study treatment
- Any TEAE with grade  $\geq 3$
- Any TEAE with grade  $\geq 3$  related to study drug or catheter with sub bullets for TEAEs with grade  $\geq 3$  related to catheter placement, lerapolturev or pembrolizumab
- Any Grade 5 TEAEs
- Any Grade 5 TEAEs related to study drug or catheter with sub bullets for Grade 5 TEAEs related to catheter placement, lerapolturev or pembrolizumab

The occurrence of TEAEs and TEAEs related to study drug or catheter will be summarized by PT, system organ class, and severity. All AEs reported will be listed for individual participants showing both verbatim and PT. All AEs that occurred prior to catheter placement will be excluded from the tables but will be included in the listings.

Missing onset dates will be imputed as previously outlined in Section 3.2.3.2 as required to determine TEAEs.

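### No planned TEAE or AESI table separates events before and after the first pembrolizumab dose, or isolates participants who received it, so the tables do not deliver the stated primary safety endpoint

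*SAP*

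**What the plan says.** The SAP calls the virus lerapolturev; the protocol calls it PVSRIPO.

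- **Start of the TEAE window.** SAP 3.2.6: "A TEAE will be an AE that occurred during the study on or after catheter placement". Protocol 8.4.5 opens it slightly later: "Summaries of TEAE will begin at the time of PVSRIPO infusion".
- **Start of pembrolizumab.** SAP 1.1: "initiated 14 days after lerapolturev infusion (up to 28 days, if necessary), given every 3 weeks, through Week 104".
- **Population and layout.** The Safety Set (SAP 4.2) is everyone enrolled who had an infusion catheter placed. SAP Section 5 presents every summary table for the overall population. SAP 5.8.1 repeats this for adverse events: "The number of participants for the following groups will be summarized by overall". Tables 14.3.1.1 to 14.3.1.11 are all titled Safety Set.
- **Repeated events.** Under SAP 5.8.1, several events in one preferred term count once, at the worst grade and the strongest relationship.
- **Stated endpoint.** SAP Section 2 defines the primary safety endpoint in participants given the virus and one or more pembrolizumab doses. Protocol 8.4.5 makes that group the primary safety analysis set and says virus-only patients will be summarized separately.
- **Recorded changes.** SAP Section 6 lists dropped analyses but does not mention these separate safety summaries.

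**The concern.** Whether adding pembrolizumab worsens edema is the trial's own safety question. Protocol 3.2 builds a dosing delay around it: "Peritumoral edema may be associated with PVSRIPO treatment and there is potential for the same after immune checkpoint inhibition". The synopsis also wants the regimen's safety judged "relative to accumulated experience with PVSRIPO alone".

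A single overall column mixes two things that the reader needs apart. The first is people: participants given both agents, those given the virus only, and any who had a catheter placed without infusion. SAP 5.6 has a category for 0 pembrolizumab cycles, so the plan foresees participants without combination exposure in this set. The second is time: the perioperative and virus-only weeks, and the period after the first pembrolizumab dose. If both are merged, the rate shown is not the rate in the endpoint's population, and a change in edema after pembrolizumab starts is invisible in the table meant to describe edema.

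**Working it through.** The plan gives no figure on this point, so the check sets its rules side by side and does the day arithmetic.

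1. **Length of the period before pembrolizumab.** The first dose falls on Day 14 to 28 after infusion. Infusion is on the day of catheter placement or the next day, and the interval "may be extended up to 72 h post-placement with Sponsor approval" (Protocol 5.2.2). From infusion the period is 14 to 28 days. From catheter placement it is 14 + 0 = 14 to 28 + 3 = 31 days.

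2. **What the SAP's start point changes.** Against the protocol's start at infusion, it adds only the gap between catheter and infusion, at most 3 days. The 14 to 28 virus-only days fall inside both windows. The start point is therefore not the cause. The cause is the missing split together with the catheter-based set.

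3. **Share of observed time before the first dose**, measured from infusion:
   - to the end of the 21-day window after the first dose: 14/(14 + 21) = 40% to 28/(28 + 21) = 57%;
   - over 6 months (183 days): 14/183 = 7.7% to 28/183 = 15.3%;
   - over 10 months (304 days): 14/304 = 4.6% to 28/304 = 9.2%;
   - over the 730-day maximum: 14/730 = 1.9% to 28/730 = 3.8%.

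   Six to ten months is the median survival range in Protocol Section 1.

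4. **What a pooled count can show.** Assume, for illustration only, independent edema risks before and after the first dose. The proportion ever affected is 1 − (1 − before)(1 − after).
   - 30% before, 10% after: 1 − 0.70 × 0.90 = 37%.
   - 10% before, 30% after: 1 − 0.90 × 0.70 = 37%.

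   A fall and a rise give the same table entry. The worst-grade rule has the same effect within a participant: Grade 2 then Grade 3 in one term, or the reverse, is a single Grade 3 entry.

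5. **Whether the endpoint's population appears in any table.** None of the eleven TEAE tables is restricted to participants given pembrolizumab or divided by its receipt.

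6. **Why a split needs person-time.** With full follow-up, the period after the first dose lasts 730 − 14 = 716 or 730 − 28 = 702 days. At an equal event rate, raw event counts after the dose would exceed those before it by 716/14 = 51 or 702/28 = 25 times. With 6 months of follow-up the ratios are 169/14 = 12 and 155/28 = 5.5. Bare counts would suggest a rise where none exists.

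**The case against.** The case for the plan has substance.

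- **The tables do not claim to show combination toxicity.** A reader might infer that surgical and virus-only events are being reported as such. The documents do not support this: the tables are titled Safety Set, and the overview divides related events by catheter, lerapolturev and pembrolizumab. This stands, but attribution is a partial remedy. It is investigator judgement, the AESI table's title shows no such division, and SAP 3.2.3.1 imputes a missing relationship as Definite for any event from catheter placement, with no exception for events before pembrolizumab.
- **Some outputs do carry timing.** DLT item 1 is tied to the 3 weeks after the first dose and feeds Table 14.3.1.8; KPS and NANO are tabulated by visit. This stands. However, that DLT item covers only Grade 3 or higher neurologic events that fail management or need debulking, and KPS and NANO are not event counts.
- **The information is collected.** Protocol 7.5.2 requires edema start and stop dates, and listings of adverse events and pembrolizumab infusions are planned. To say that the trial cannot answer the question would go too far. What is missing is a planned summary.
- **Counting from the first component of a sequential regimen is legitimate**, and it suits a comparison with external PVSRIPO-alone data. This is a reason to keep the overall column.
- **SAP 4.2 says the set is analyzed by treatment received.** Read alone, that could imply separate groups, but Section 5 and 5.8.1 present only the overall population.

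A reader might also take the protocol to call edema attribution difficult. Sections 7.4 and 7.5.2 list several possible causes, and 7.5.2 asks that onset timing be considered; neither says that. The remark about difficulty in 8.4.6.1 concerns imaging.

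**Conclusion.** The point holds as a gap in the planned tables. All eleven TEAE tables, including the AESI table, pool participants with and without pembrolizumab and pool onset before and after the first dose. They therefore do not deliver the primary safety endpoint as SAP Section 2 and Protocol 8.4.5 define its population, and SAP Section 6 does not record the departure. They also cannot show whether edema is new or worse after pembrolizumab starts.

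The affected period is 14 to 28 days per participant from infusion: a small share of total follow-up, but 40% to 57% of the early window in which the combination is first judged. This rests on the scheduled dosing days. The 37% example rests on assumed, independent risks and is not a forecast.

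A reader might scale the Phase 1 expansion figure, 19% of 31 patients with related Grade 3 or higher events, to this trial to count events unrelated to pembrolizumab. The documents do not support that as a measure of this gap: the figure has no onset window, and SAP Section 6 says planned enrollment was not reached without giving the number. The number of events falling before the first dose is unknown.

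The change is worth making because it affects what the primary safety tables can show and uses data already collected.

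**What to change.** In SAP 5.8.1, for Tables 14.3.1.1, 14.3.1.2, 14.3.1.4 and 14.3.1.9, keep the overall column and add:

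1. A column for participants given both agents (one or more pembrolizumab doses), split within those same participants into (a) onset from catheter placement to before the first pembrolizumab dose and (b) onset from that dose onward, counting events that are new or worse than the grade just before it. Give person-time or exposure-adjusted rates for each period.
2. A separate column for participants given lerapolturev only.

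Participants with a catheter but no infusion stay in the overall column, with a footnote that the columns do not add up to it.

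In SAP 3.2.3.2, state which drug's dose date completes a partial onset date for this split. The present rule refers to a single study-drug dose date, while SAP 5.6 counts both agents as study drug. Using the infusion date would place events with wholly missing onset dates before pembrolizumab.

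Record any remaining departure from Protocol 8.4.5 in SAP Section 6.

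Label the before/after comparison descriptive. It is confounded with time since infusion: Protocol 6.2.2.1 describes virus-related edema effects within 12 months. It is also selective: under Protocol 3.2, participants whose edema has not resolved by Week 4 never receive pembrolizumab.

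The cost is extra columns programmed from dates already collected. The downside is small counts per column, in a trial that enrolled fewer than planned.
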